#### 7 STATISTICAL ANALYSES

#### 7.1 General Methods

Unless otherwise noted, discrete variables will be tabulated by the frequency and proportion of subjects falling into each category, grouped by treatment. Percentages given in these tables will be rounded to the first decimal and, therefore, may not always sum to 100%. Percentages less than 0.1 will be indicated as '< 0.1'. Continuous variables will be summarized by treatment group using the mean, standard deviation, median, minimum, and maximum values.

Time-to-event variables (e.g. time-to resolution) will be analyzed using the Kaplan-Meier technique. When specified, the median will be reported along with 95% CI using Brookmeyer and Crowley method (using log-log transformation for constructing the confidence intervals).

The conventions to be used for imputing missing and partial dates for analyses requiring dates are described in Section 8.

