#### 7.6.6.3 Time-to Resolution of Select AE

Time-to resolution of the following specific events will be summarized separately for each category/subcategory.

- Time-to resolution of drug-related select AE (any grade, grade 3-5) by treatment group
- Time-to resolution of drug-related select AE (any grade, grade 3-5) where immune modulating medication was initiated, by treatment group

Time-to resolution analyses are restricted to treated subjects who experienced the specific events. Time-to resolution where immune modulating medication was initiated analyses are restricted to treated subjects who experienced the specific events and who received immune modulating medication during the longest select AE.

The analyses will be conducted using the 30-day safety window.

The following summary statistics will be reported: percentage of subjects with resolution of the longest select AE, median time-to resolution along with 95% CI (derived from Kaplan-Meier estimation) and ranges.

See time-to resolution definition subsection of APPENDIX 1 for additional details.

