# 7.6.7 Immune-Mediated Adverse Events (US Submission)

IMAEs will be summarized by treatment group for each immune-mediated category / PT using the 100-day safety window:

- Overall summary of non-endocrine IMAEs by worst CTC grade (any grade, grade 3-4, grade 5) where immune modulating medication was initiated presented by Category / PT.
- Overall summary of endocrine IMAEs by worst CTC grade (any grade, grade 3-4, grade 5) presented by Category / PT.
- Overall summary of non-endocrine IMAEs leading to discontinuation by worst CTC grade (any grade, grade 3-4, grade 5) where immune modulating medication was initiated presented by Category / PT.
- Overall summary of endocrine IMAEs leading to discontinuation by worst CTC grade (any grade, grade 3-4, grade 5) presented by Category / PT.
- Overall summary of non-endocrine IMAEs leading to dose delay or reduction by worst CTC grade (any grade, grade 3-4, grade 5) where immune modulating medication was initiated presented by Category / PT
- Overall summary of endocrine IMAEs leading to dose delay or reduction by worst CTC grade (any grade, grade 3-4, grade 5) presented by Category / PT.
- Summaries of time-to onset and time-to resolution of non-endocrine IMAEs where immune modulating medication was initiated presented by Category.
- Summaries of time-to onset and time-to resolution of endocrine IMAEs presented by Category.

A by-subject listing of IMAEs will be provided. By-subject listings of time-to resolution for longest IMAEs cluster (any grade and grade 3-5 in separate summaries) will also be provided. For new studies which collect investigator assessment of potential IMAE data, a by-subject listing of AEs considered as immune-mediated events per investigator but not qualified for IMAEs definition will also be provided.

In addition, for all nivolumab treated subjects who experienced at least one IMAE, the following data presentation will be provided:

- Summary of subjects who were re-challenged with nivolumab by IMAE category, with extended follow-up
- Summary of subjects who were re-challenged with nivolumab or ipilimumab by IMAE category, with extended follow-up

For these, re-challenge is considered to have occurred when last nivolumab and/or ipilimumab infusion was administered after the onset of an IMAE.

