#### Time-to resolution definition

In order to derive the time-to resolution, overlapping or contiguous AEs within a specific category or subcategory will be collapsed into what will be termed "clustered" AEs. For example, if a subject (without pre-treatment AE) experienced an AE from 1st to 5th January, another AE (with different PT but within same category) from 6th to 11th January and same AE from 10th to 12th January, these will be collapsed into one clustered AE from 1st to 12th January. Table A1-1 is summarizing key derivation steps for each type of clustered AEs.

Time-to resolution of AE (any grade) for a specific category is defined as the longest time from onset to complete resolution or improvement to the grade at baseline among all clustered AEs experienced by the subject in this category per adverse event criteria category. Events which worsened into grade 5 events (death) or have a resolution date equal to the date of death are considered unresolved. If a clustered AE is considered as unresolved, the resolution date will be censored to the last known alive date. Improvement to the grade at baseline implies that all different events in the clustered adverse event should at least have improved to the corresponding (i.e. with same preferred term) baseline grade. This measure is defined only for subjects who experienced at least one AE in the specific category.

The time-to resolution of AE (grade 3-5) for a specific category is defined similarly with an onset date corresponding to a grade 3-5 AE.

Time-to resolution of drug-related AE (any grade or grade 3-5) for a specific category is defined similarly but restricted to drug-related AE.

The time-to resolution of AE (any grade or grade 3-5, drug-related or all) where immune modulating medication was initiated is defined similarly. For data presentation not restricted to IMAE, the additional condition that the subject started an immune modulating medication during the longest AE resolution period will be applied.

Time-to resolution for a specific subcategory is defined similarly but restricted to event of this subcategory.

**Table A1-1:** Derivation of Clustered AE

Derivation
Collapse any on-treatment AE from the same category
Collapse any on-treatment drug-related
AE from the same category
Collapse any on-treatment AE from the same category.

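### The Kaplan-Meier median time to resolution of select and immune-mediated AEs censors deaths with the AE unresolved, so it leans towards faster resolution, mainly for slow-resolving categories

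*SAP*

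**What the plan says.** SAP Appendix 1 (Time-to resolution definition) merges overlapping or adjacent AEs of one category into clusters and takes each subject's longest cluster. On death it says: "Events which worsened into grade 5 events (death) or have a resolution date equal to the date of death are considered unresolved". The next sentence gives the handling: "If a clustered AE is considered as unresolved, the resolution date will be censored to the last known alive date". For a subject who died, that date is in effect the date of death.

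For select AEs, Section 7.6.6.3 reports "percentage of subjects with resolution of the longest select AE, median time-to resolution along with 95% CI (derived from Kaplan-Meier estimation) and ranges", for any grade and again for grade 3-5. The denominator is set by this sentence: "Time-to resolution analyses are restricted to treated subjects who experienced the specific events".

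For immune-mediated AEs, Section 7.6.7 plans "Summaries of time-to onset and time-to resolution of non-endocrine IMAEs where immune modulating medication was initiated presented by Category" and "Summaries of time-to onset and time-to resolution of endocrine IMAEs presented by Category" without itemising the statistics. The general rule in Section 7.1 then applies: "Time-to-event variables (e.g. time-to resolution) will be analyzed using the Kaplan-Meier technique". No competing-risk analysis of resolution is planned anywhere in the SAP.

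**The concern.** Kaplan-Meier treats a censored subject as someone who would go on to resolve at the same rate as those still observed. That is reasonable for a participant alive with an ongoing AE at data cutoff. It is not reasonable for one who has died, because death rules out resolution. Removing such subjects from the risk set at death leaves a median describing a hypothetical setting in which nobody dies before resolving.

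Three features of this trial make the rule relevant. The planning median survival is short (13 and 10.8 months, SAP Table 5-1), so deaths with an AE still open are to be expected. The separate grade 3-5 summaries contain the fatal events by construction, and these enter as censored times. Endocrine immune-mediated AEs get their own resolution summary; if they resolve slowly, that is where the rule would matter most.

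At stake is how quickly immunotherapy toxicity appears to reverse in tables prepared for the EU and US submissions.

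**Working it through.** The SAP states no resolution figure, so there is nothing to reproduce. The check establishes direction first and then illustrates size.

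**Direction.** On the same data, one minus the Kaplan-Meier curve with deaths censored is never below the cumulative incidence of resolution with death as a competing event. The Kaplan-Meier median is therefore never longer than the competing-risk median.

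**Size, illustration 1: constant hazards.**

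- Death median: 13 and 10.8 months, from Table 5-1. These are medians from randomisation and serve only to scale the hazard after AE onset. A 3-month median after onset is added as an assumed severe case.
- Resolution median *m*: not in the documents; assumed 4 to 48 weeks.
- Hazards: r = ln2/m for resolution and d = ln2/(death median) for death. With 30.4375 days per month (SAP Section 8), 13 months is 13 × 30.4375/7 = 56.5 weeks.
- Kaplan-Meier median with deaths censored: m.
- Competing-risk median: −ln(1 − 0.5(r+d)/r)/(r+d), which exists only if r/(r+d), the proportion ever resolving, exceeds one half.

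Worked case, m = 24 weeks and death median 13 months: r = 0.02888 and (r+d)/r = 1 + 24/56.5 = 1.425, so r+d = 0.0411. The median is −ln(1 − 0.712)/0.0411 = 30.3 weeks.

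| KM median (weeks) | Competing-risk median, death median 13 months | 10.8 months | 3 months (assumed) |
|---|---|---|---|
| 4 | 4.1 | 4.2 | 4.7 |
| 8 | 8.6 | 8.7 | 11.8 |
| 12 | 13.3 | 13.6 | 29.0 |
| 24 | 30.3 | 32.3 | not reached |
| 48 | 96.8 | not reached | not reached |

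In months, at a death median of 13: 2.0 becomes 2.15, and 12.0 becomes 29.3.

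**Size, illustration 2: a share of AEs fatal early.** Assumed: fatal AEs end in death with median 2 weeks and the others resolve with median 8 weeks (simulation, 200,000 subjects).

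| Fatal share | KM median (weeks) | Median with fatal AEs counted as never resolved (weeks) | Crude % resolved |
|---|---|---|---|
| 2% | 8.1 | 8.2 | 98 |
| 5% | 8.2 | 8.6 | 95 |
| 10% | 8.4 | 9.3 | 90 |
| 20% | 8.7 | 11.3 | 80 |
| 30% | 9.2 | 14.4 | 70 |

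The last column does not depend on how deaths are censored. Fatal AEs stay in the denominator as unresolved, so with 10% fatal the percentage is 90 under either analysis.

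**The case against.** The best reply is that the SAP reports more than the median. The percentage resolved stands beside it and already counts deaths against resolution. Deaths are tabulated overall and within 30 and 100 days of last dose (Section 7.6.1), select and immune-mediated AEs have grade 5 columns (Sections 7.6.6.1 and 7.6.7), and by-subject resolution listings are planned for the longest immune-mediated cluster. If most AEs resolve within weeks and few are fatal, the median hardly moves: 8 against 8.6 weeks. All of this stands and keeps the point small. None of it corrects the median where resolution is slow or many die with the AE open.

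A reader might infer three stronger things, which the documents do not support.

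- *Toxicity is reported as resolving more often than it does.* The percentage in Section 7.6.6.3 is a crude proportion, and the censoring rule does not raise it. It can be raised only through the longest-cluster rule, when a subject's longest cluster resolved and a shorter one in the same category was fatal or unresolved. The size of that effect is unknown and probably small.
- *Resolution probabilities are overstated by many percentage points.* At 12 months, with a death median of 13 months and net resolution of 30, 50 or 80%, one minus Kaplan-Meier exceeds the cumulative incidence by about 7, 12 or 16 points. The SAP lists no fixed-time resolution probability, so these gaps concern an output that is not planned.
- *The definition always favours the drug.* Taking the longest cluster generally lengthens a subject's resolution time, which works the other way.

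**Conclusion.** The point holds for the Kaplan-Meier median. That statistic is explicit for select AEs and follows from Section 7.1 for immune-mediated AEs. Its bias has a known direction, towards faster resolution, and an unknown size.

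Under constant hazards and a death median of 13 months, the shortfall relative to the competing-risk median is about 2 to 10% for AEs with a Kaplan-Meier median of 4 to 12 weeks (4 against 4.1; 12 against 13.3). It is about a fifth at 24 weeks (24 against 30.3) and about half at 48 weeks (48 against 96.8). It grows if survival after AE onset is short. These figures rest on assumed resolution rates, on a death hazard borrowed from the planning medians, and on independence of the two hazards from time; they are illustrations, not estimates for this trial.

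Severity is minor. The output is a descriptive safety summary with no bearing on the primary endpoints, alpha or power. It is still worth changing because a stated rule yields a biased statistic and the remedy is nearly free. The SAP already takes account of death in a comparable place: Section 7.9.2 analyses time to symptomatic deterioration or death beside deterioration alone.

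**What to change.** In Appendix 1, Section 7.6.6.3 and Section 7.6.7:

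- Treat death with an unresolved cluster, including grade 5 events, as a competing event. Keep censoring for subjects who are alive with an ongoing AE.
- Report the Aalen-Johansen cumulative incidence of resolution and its median, by category and arm.
- Show the number of subjects who died with the AE ongoing next to the median.
- Do not count a subject as resolved in a category if any cluster in it was fatal.
- Keep the Kaplan-Meier median beside the new one if comparability with earlier programme tables is wanted, labelled as censoring deaths.

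The cost is SAP wording, a standard procedure on data already collected, and one added summary. Some resolution figures will look slightly less favourable.

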4.5.1 Dosing

4.5.1.1 Nivolumab plus Ipilimumab (Arm A)

Participants randomized to Arm A will receive treatment with nivolumab 3 mg/kg every 2 weeks as a 30-minute infusion and ipilimumab 1 mg/kg every 6 weeks as a 30-minute infusion, starting on Day 1, until progression, unacceptable toxicity, withdrawal of consent, the study ends, or a maximum of 24 months from the first study treatment, whichever occurs first.

When nivolumab and ipilimumab are to be administered on the same day, separate infusion bags and filters must be used for each infusion. Nivolumab is to be administered first. The second infusion will always be ipilimumab and will start no sooner than 30 minutes after completion of the nivolumab infusion. Participants who require small volumes may infuse over < 30 minutes but no less than 20 minutes. The second infusion will always be the ipilimumab study treatment and will start after the infusion line has been flushed, filters changed and participant has been observed to ensure no infusion reaction has occurred.

Nivolumab and ipilimumab may be diluted in 0.9% Sodium Chloride Solution or 5% Dextrose solution.

Dosing calculations should be based on the body weight. If the participant's weight on the day of dosing differs by > 10% from the weight used to calculate the prior dose, the dose must be recalculated. All doses should be rounded to the nearest milligram. There will be no dose modifications allowed for both nivolumab and ipilimumab.

Participants may be dosed with nivolumab no less than 12 days from the previous dose. There are no premedications recommended for the first dose of study drug.

Participants should be carefully monitored for infusion reactions during nivolumab administration. If an acute infusion reaction is noted, participants should be managed according to [Section 4.5.8](#)

Doses of nivolumab may be interrupted, delayed, or discontinued depending on how well the participant tolerates the treatment. Dosing visits are not skipped, only delayed.

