The recommended premedication are dexamethasone (dosing according to local standard; an equivalent dose of another corticosteroids may be substituted) and a 5-HT3 receptor antagonist (type per investigator discretion and local standards of care) prior to each dose. Additional use of emetics premedication may be employed at the discretion of the investigator. Refer to the local product label for more detail.

For cisplatin:

Hydration guidelines may be modified at the discretion of the treating physician provided adequate pre- and post-cisplatin hydration is achieved, and renal function remains adequate. One suggested regimen consists of administering cisplatin in 500 cc to 1000 cc of IV fluids following adequate hydration and the establishment of adequate urinary output. It is suggested the pre-cisplatin hydration consist of NS at 500 cc/hr x 1 liter and post-cisplatin hydration consist of 1/2 NS + 10 meq KCl/liter + 1 gram magnesium sulfate/liter + 25 grams mannitol/liter at 500 cc/hr for at least one hour, followed by additional hydration at the discretion of the investigator.

It is suggested that patients receive antiemetic therapy, acute and delayed, including dexamethasone, 5-HT3 serotonin receptor antagonists. However, the specifics of the regimen are at the discretion of the treating physician, provided adequate control is achieved. One potential regimen consists of 20 mg of oral or IV dexamethasone and a high dose of oral or IV 5-HT3 antagonist (such as 2 mg oral or 10 mg/kg IV granisetron, or 32 mg oral or IV ondansetron) on the day of cisplatin administration. Followed by additional anti-emetics consisting of oral dexamethasone and scheduled 5-HT3 serotonin receptor antagonists on days 2-5. For example, 8 mg orally, twice daily for days 2 and 3, and then 4 mg orally, twice daily for days 4 and 5, especially if aprepitant is not given.

All supportive measures consistent with optimal patient care should be used throughout the study. Recombinant erythropoietin or similar compound may be administered for symptomatic and/or progressive > Grade 2 anemia. Agents such as G-CSF may also be used at the investigators' discretion.

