## 7.4.3.1 Immune Modulating Medication

Immune modulating concomitant medications are medications entered on an immune modulating medication form or available from the most current pre-defined list of immune modulating medications. The list of anatomic class, therapeutic class and generic name used for the selection at the time of the database lock will be provided.

The percentage of subjects who received immune modulating concomitant medication for

- management of adverse event
- premedication
- other use
- any use
- management of drug-related select adverse event (any grade, grade 3-5) by select AE category/subcategory (EU Submission)
- management of IMAEs (any grade, grade 3-5) by IMAE category (US Submission)

will be reported separately for each treatment group (percentages of treated subjects by medication class and generic term).

For each category/subcategory of drug-related select AEs (any grade, grade 3-5) and IMAEs (any grade, grade 3-5), the following will be reported for each treatment group:

• The total immune modulating medication treatment duration (excluding overlaps), duration of high dose of corticosteroid, initial dose of corticosteroid, and tapering duration (summary statistics)

Duration represents the total duration the subject received the concomitant medication of interest. If the subject took the medication periodically, then DURATION is the summation of all use. Initial dose represents the dose of the concomitant medication of interest received at the start of the event. In the case multiple medications started on the same date, the highest equivalent dose is chosen and converted to mg/kg by dividing by the subject's recent weight.

These analyses, except the ones related to IMAEs will be conducted using the 30-day safety window. The analyses related to IMAEs will be conducted using the 100-day safety window.

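### The select-AE time-to-resolution subset with immune modulating medication is chosen by timing, not purpose, so Arm B events can enter through antiemetic dexamethasone alone

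*SAP*

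**What the plan says.** SAP 7.6.6.3 plans two by-arm summaries of time to resolution for drug-related select AEs. One covers all such events. The other covers the subset "where immune modulating medication was initiated, by treatment group".

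Entry to the subset is worded in two places:

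- SAP 7.6.6.3 restricts it to treated subjects with the event "who received immune modulating medication during the longest select AE".
- SAP Appendix 1 (Time-to resolution definition), for presentations not restricted to IMAEs, says that "the additional condition that the subject started an immune modulating medication during the longest AE resolution period will be applied".

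SAP 7.4.3.1 defines the drug class by how it is recorded: "Immune modulating concomitant medications are medications entered on an immune modulating medication form or available from the most current pre-defined list of immune modulating medications". That section reports "duration of high dose of corticosteroid, initial dose of corticosteroid, and tapering duration", and it names premedication as one use of the class, separate from management of an adverse event.

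The two arms differ in routine steroid exposure. For platinum in Arm B, protocol 4.5.1.2 states: "The recommended premedication are dexamethasone (dosing according to local standard". This applies before each dose, every 3 weeks for at most 6 cycles, and one potential cisplatin regimen continues dexamethasone through day 5. For Arm A, protocol 4.5.1.1 states: "There are no premedications recommended for the first dose of study drug". It specifies no routine steroid antiemetic.

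**The concern.** The label of the subset implies that the events in it were treated with immunosuppression. The rule does not deliver that. A drug-related gastrointestinal select AE in Arm B that spans a platinum day would satisfy it through that cycle's dexamethasone, even if nothing was given for the event. The same event in Arm A would normally enter only if a steroid was given for it.

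Two features make this more than loose wording. The routine exposure that triggers entry sits in one arm. And the chance of spanning a dexamethasone start rises with event length, which is the quantity the table reports. The analysis also takes the longest clustered event per category, which favours events long enough to span a start. Both the number of Arm B events and their median time to resolution are exposed, and a reader comparing arms could take the Arm B figures as describing steroid-managed toxicity.

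**Working it through.** The documents give no figure for this, so there is none to reproduce. The check traces the rule and then illustrates its size.

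**Does the rule require a purpose?** No. Appendix 1 requires a start during the event and 7.6.6.3 requires receipt. The verbs also differ: a steroid begun before the event and continued into it counts as received but not as started. By contrast, SAP 7.6.5 tabulates AEs that needed such medication, and SAP 7.1.1.3 defines non-endocrine IMAEs as treated with it. The SAP therefore uses a purpose link elsewhere but not here.

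**Is antiemetic dexamethasone in the class?** This is inferred. SAP 7.4.3.1 reports corticosteroid measures for the class and expects premedication records in it. The pre-defined list and the CRF form are not in the documents.

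**When does it act?** Platinum is given every 21 days for up to 6 cycles. The last Day 1 is study day 1 + 5 × 21 = 106, and the platinum phase lasts 6 × 3 = 18 weeks, without delays.

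**How often would an untreated Arm B event qualify?** Assume onset is uniform over the 21-day cycle, there are no delays, and dexamethasone is recorded cycle by cycle. An event covers D calendar days. Each share is capped at 1.

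- One recorded start per cycle, on day 1: share = D/21.
- Separate start records on days 1, 2 and 4 (when the example regimen changes dose): share = (D + 3)/21.
- Received wording, dosing on days 1 to 5: share = (D + 4)/21.

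| Event length D | One start per cycle | Starts on days 1, 2, 4 | Received, days 1–5 |
|---|---|---|---|
| 3 days | 3/21 = 14% | 6/21 = 29% | 7/21 = 33% |
| 7 days | 7/21 = 33% | 10/21 = 48% | 11/21 = 52% |
| 14 days | 14/21 = 67% | 17/21 = 81% | 18/21 = 86% |
| 21 days or more | 100% | 100% | 100% |

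Enumerating all 21 onset days gives the same shares. The corresponding Arm A share from routine antiemetics is 0%.

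**Selection on length.** In the one-start column, 7-, 14- and 21-day events enter in the ratio 1 : 2 : 3. If the three lengths were equally common (an assumption for illustration only), their mean would be 14 days. The mean among those admitted through dexamethasone would be (7 × 1 + 14 × 2 + 21 × 3)/6 = 98/6 = 16.3 days.

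**The case against.** The strongest reply is that this is one secondary, descriptive presentation and that the SAP answers the more important question elsewhere. Much of that stands, and it rules out several stronger readings.

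- A reader might infer that the control arm's frequency of steroid-managed toxicity is overstated. The documents do not support this. SAP 7.4.3.1 reports the percentage of subjects given the medication to manage drug-related select AEs by category, apart from premedication and other use. SAP 7.6.5 also reports by need. The select-AE incidence section, 7.6.6.1, lists no table using the timing rule.
- A reader might infer that Arm A events stay out of the subset. They do not. They enter when treated with steroids, and occasionally through prophylaxis: after a Grade 2 infusion reaction (protocol 4.5.8.1) or in short permitted courses such as for contrast allergy (protocol 3.4.3). The 0% above concerns routine antiemetics only, and the Arm A statement on premedication is limited to the first dose.
- A reader might infer that the 7.4.3.1 duration summary counts every antiemetic day, up to 6 × 5 = 30 days. The sentence "If the subject took the medication periodically, then DURATION is the summation of all use" can be read that way. But the surrounding text speaks of the medication of interest, per select AE category, directly after the items on management of events, so the wording is ambiguous. The 30 days also rest on what the protocol offers as one potential cisplatin regimen.
- A reader might infer that the Arm B subset would mostly reflect antiemetic scheduling. The shares are illustrative. A single continuous or as-needed dexamethasone record would give one start, not six.

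The reply does not supply the missing link between drug and event. Followed literally, the rule still admits Arm B events that were not treated with steroids.

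**Conclusion.** The point holds for one analysis: time to resolution of drug-related select AEs in the immune-modulating-medication subset. Entry there depends on timing alone, routine steroid exposure is recommended in Arm B only, and the selection favours longer events. The Arm B count and median resolution time can both be distorted. Illustratively, 33% of 7-day events, 67% of 14-day events and 100% of events of 21 days or more would qualify during platinum cycles with no treatment given for them.

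This rests on dexamethasone being on a list that the documents do not contain, and on uniform onset, undelayed 21-day cycles and one recorded start per cycle. The effect is confined mainly to the platinum phase and to the longest clustered event per category. IMAE presentations and the purpose-linked frequency tables are outside it. No test or error rate is involved. It is still worth correcting before lock, because a stated rule builds a by-arm, length-dependent selection into a table whose label suggests treated events.

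**What to change.** In both SAP 7.6.6.3 and Appendix 1:

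- Require that the medication was started during the event and recorded as given to manage that select AE. Exclude premedication and other use.
- Tie the drug to that particular event. A filter on management of any adverse event would still admit dexamethasone recorded as treatment for platinum-induced vomiting.
- Use one verb in both places, so that started and received no longer define different subsets.
- Set a default for records with missing indication.

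In SAP 7.4.3.1, state that duration, initial dose and taper per select AE category count only courses given to manage that event.

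With this change the shares in the table fall to 0% for antiemetic dexamethasone alone, and events treated with immune modulating medication stay in for both arms. The cost is SAP wording, minor programming and a few records with missing indication. SAP 7.4.3.1 already plans summaries by purpose and select AE category, so the data should carry the link. Nothing changes in dosing or clinical management.
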